**Table 3: Schedule of Activities: Part C (Pivotal)**

	Screening 	Loading Dose Treatment Period									Maintenance Treatment Period			EOS Visit 	Safety FU (Alternative EOS) Visit  (In Person or Telephone Contact)
		Baseline (Dose 1)			Week 2 (Dose 2)			Week 4 (Dose 3)			Week 8, 12, 16, 20, and 24				
Tests and Assessments 	Day -28 to Day -1	Day 1 (±3 days)			Day 15 (±3 days)			Day 29 (±3 days)			Days 57, 85, 113, 141, and 169 (±3 days)			Day 197 OR 4 Weeks After Last Dose (±3 days)	Day 225 OR 8 Weeks After Last Dose (±3 days)
		Pre dose	LP	Post dose	Pre dose	LP	Post dose	Pre dose	LP	Post dose	Pre dose	LP	Post dose		
Informed Consent (main) 	X														
Medical History	X														
Confirmation of Eligibility Criteria	X	X													
Randomization		X													
Telephone Contact 				X			X			X			X		
Ventilation Use 		X			X			X			X			X	
ALSFRS-R 	X	X			X			X			X			X	
SVC 	X	X			X			X			X			X	
HHD 		X			X			X			X			X	

CONFIDENTIAL

The information contained herein may not be used, disclosed, or published without the written consent of Biogen MA Inc.

	Screening 	Loading Dose Treatment Period									Maintenance Treatment Period			EOS Visit 	Safety FU (Alternative EOS) Visit  (In Person or Telephone Contact)
		Baseline (Dose 1)			Week 2 (Dose 2)			Week 4 (Dose 3)			Week 8, 12, 16, 20, and 24			Week 28 OR (4 Weeks After Last Dose)	Week 32 OR (8 Weeks After Last Dose)
Tests and Assessments 	Day -28 to Day -1	Day 1 (±3 days)			Day 15 (±3 days)			Day 29 (±3 days)			Days 57, 85, 113, 141, and 169 (±3 days)			Day 197 OR 4 Weeks After Last Dose (±3 days)	Day 225 OR 8 Weeks After Last Dose (±3 days)
		Pre dose	LP	Post dose	Pre dose	LP	Post dose	Pre dose	LP	Post dose	Pre dose	LP	Post dose		
C-SSRS Questionnaire 		X							X 				X 		X 
Height	X														
Weight 	X	X										X		X	

CONFIDENTIAL

The information contained herein may not be used, disclosed, or published without the written consent of Biogen MA Inc.

	Screening 	Loading Dose Treatment Period									Maintenance Treatment Period	EOS Visit 	Safety FU (Alternative EOS) Visit  (In Person or Telephone Contact)		
		Baseline (Dose 1)			Week 2 (Dose 2)			Week 4 (Dose 3)			Week 8, 12, 16, 20, and 24	Week 28 OR (4 Weeks After Last Dose)	Week 32 OR (8 Weeks After Last Dose)		
Tests and Assessments 	Day -28 to Day -1	Day 1 (±3 days)			Day 15 (±3 days)			Day 29 (±3 days)			Days 57, 85, 113, 141, and 169 (±3 days)			Day 197 OR 4 Weeks After Last Dose (±3 days)	Day 225 OR 8 Weeks After Last Dose (±3 days)
		Pre dose	LP	Post dose	Pre dose	LP	Post dose	Pre dose	LP	Post dose	Pre dose	LP	Post dose		
Vital Signs (temperature, blood pressure, pulse rate, respiratory rate) 	X	X		X	X		X	X		X	X		X	X	
12-Lead ECG 	X	X		X 							X 		X 	X	
Physical Examination 	X	X			X 			X 			X 			X 	
Limited Neurological Examination 	X	X		X	X		X	X		X	X		X	X	
MMSE	X	X		X							X 		X 	X	
FSH Test 	X														
Pregnancy Test 	X (serum)	X			X			X			X			X (serum)	
Blood Sampling for HIV, HCV, and HBV Testing	X														

CONFIDENTIAL

The information contained herein may not be used, disclosed, or published without the written consent of Biogen MA Inc.

	Screening 	Loading Dose Treatment Period									Maintenance Treatment Period	EOS Visit 	Safety FU (Alternative EOS) Visit  (In Person or Telephone Contact)		
		Baseline (Dose 1)			Week 2 (Dose 2)			Week 4 (Dose 3)			Week 8, 12, 16, 20, and 24	Week 28 OR (4 Weeks After Last Dose)	Week 32 OR (8 Weeks After Last Dose)		
Tests and Assessments 	Day -28 to Day -1	Day 1 (±3 days)			Day 15 (±3 days)			Day 29 (±3 days)			Days 57, 85, 113, 141, and 169 (±3 days)			Day 197 OR 4 Weeks After Last Dose (±3 days)	Day 225 OR 8 Weeks After Last Dose (±3 days)
		Pre dose	LP	Post dose	Pre dose	LP	Post dose	Pre dose	LP	Post dose	Pre dose	LP	Post dose		
Clinical Laboratory Samples for Hematology, Coagulation, Chemistry, and Urinalysis 	X	X			X			X			X			X	

CONFIDENTIAL

The information contained herein may not be used, disclosed, or published without the written consent of Biogen MA Inc.

	Screening 	Loading Dose Treatment Period									Maintenance Treatment Period	EOS Visit 	Safety FU (Alternative EOS) Visit  (In Person or Telephone Contact)		
		Baseline (Dose 1)			Week 2 (Dose 2)			Week 4 (Dose 3)			Week 8, 12, 16, 20, and 24	Week 28 OR (4 Weeks After Last Dose)	Week 32 OR (8 Weeks After Last Dose)		
Tests and Assessments 	Day -28 to Day -1	Day 1 (±3 days)			Day 15 (±3 days)			Day 29 (±3 days)			Days 57, 85, 113, 141, and 169 (±3 days)			Day 197 OR 4 Weeks After Last Dose (±3 days)	Day 225 OR 8 Weeks After Last Dose (±3 days)
		Pre dose	LP	Post dose	Pre dose	LP	Post dose	Pre dose	LP	Post dose	Pre dose	LP	Post dose		
Study Drug Administration 			X			X			X			X			
AE and Concomitant Therapy and Procedures Recording		-----X (ongoing)-----													
SAE Recording		-----X (ongoing)-----													

[figure not shown]
 Some sites may only participate in screening procedures.

 After completing the EOS Visit, participants will be considered study completers and will have the option to participate in the LTE study 233AS102 (see Section 7.5).

 Participants who terminate early (i.e., discontinue both study treatment and assessments) will be asked to complete the assessments of the EOS Visit within 4 weeks after the last dose of study treatment (see Section 10.1).

[figure not shown]
 Participants who do not roll over into the LTE study will have an additional safety FU visit at Week 32 or 8 weeks after the last dose of study treatment. For participants with delays between their Week 28 Visit and enrollment in the LTE study, a Safety FU (Alternative EOS) Visit will be conducted (either in person or by telephone contact) to collect AEs, SAEs, and concomitant medications or procedures. This Safety FU (Alternative EOS) Visit can be performed at Week 32 or prior to (within 2 days) enrollment in the LTE, whichever comes first.

 All visits are expected to take place on site unless participants are unable to travel to the site; then, a home visit may be possible at the discretion of the Investigator.

CONFIDENTIAL

The information contained herein may not be used, disclosed, or published without the written consent of Biogen MA Inc.

-  Telephone contact to be performed approximately 24 hours after LP.
-  Predose assessments can be performed in a single visit up to 2 days prior to dosing.
-  Participants will use a diary/eDiary to record ventilation use. The diary/eDiary should be completed only for days when the participant uses mechanical ventilation. This diary/eDiary will be reviewed with study site staff at each visit.
-  If a facemask is used at screening and/or baseline it should be used for all SVC assessments for the duration of the study. If a facemask is not used at screening and/or baseline it should not be used for the duration of the study. Upright SVC will be determined by performing 3 to 5 measures. The results will be overread by a central reader to confirm that these criteria (at least 3 acceptable tests with the 2 highest acceptable (largest and next largest) efforts within 150 mL of vital capacity) have been achieved.
-  To be performed on Week 12 (Day 85) and Week 24 (Day 169) only.
- 
-  Use “Since Last Visit” version of C-SSRS.
-  Assessment must occur on the day of dosing.
-  Temperature, systolic and diastolic blood pressure, pulse rate and respiratory rate will be measured after the participant has rested in a sitting position for at least 5 minutes.
-  Triplicate 12-lead ECGs will be obtained after the participant has rested in a supine position for at least 10 minutes. All ECGs will be centrally read; ECGs will be read by the Investigator at collection and then sent to a central ECG reader for further evaluation and to confirm eligibility at Screening. The first ECG will be interpreted, and the last 2 will be checked for consistency and quality.
-  To be assessed just prior to drawing PK blood samples at 2, 4, and 6 hours postdose on Day 1 and Day 85 only.
-  Limited physical examination will be conducted at the Investigator’s discretion.
-  The components of the limited neurological examination include motor, reflexes, and coordination/cerebellar function.
-  To confirm postmenopausal status (in postmenopausal female participants only).
-  Results from urine or serum pregnancy tests must be reviewed predose in order to determine if dose should be administered or held.
-  For women of childbearing potential only. Serum test to be performed at Screening and EOS Visit; urine or serum test to be performed at all other timepoints.
-  The results of most recent (i.e., obtained at previous visit) centrally read coagulation tests and platelet count must be reviewed before LP can be performed. Coagulation tests may be repeated at local laboratory once if, in the opinion of the Investigator, values of the initial tests are out of range but deemed not clinically significant).
-  CSF samples collected during the LP procedure will be analyzed to evaluate for blood contamination. CSF samples for safety will be tested at local laboratories.
- 

 Participants will remain at the study site for at least 1 hour postdose for safety monitoring and can be discharged at the discretion of the Investigator and in compliance with the institutional requirements once the participants have adequately recovered from the dosing procedure.

CONFIDENTIAL

The information contained herein may not be used, disclosed, or published without the written consent of Biogen MA Inc.

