#### **Part C: Screening-Only Sites**

Some sites may be designated as screening-only sites and will only perform screening visit assessments. Participants who complete screening at screening-only sites and are deemed eligible for participation in Part C will be transferred to a full participation site for the remainder of the study. Participants may also be screened at full treatment sites and transferred to other full treatment sites for randomization.

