#### **13.1.2. Slow Vital Capacity**

Vital capacity will be measured by means of an SVC test, administered in the upright position. The procedure will be performed according to the study Pulmonary Procedure Manual. Upright SVC will be determined by performing 3 to 5 measures, in accordance with criteria established by the American Thoracic Society and the European Respiratory Society [Miller 2005; Pellegrino 2005; Wanger 2005]. The results will be overread by a central reader to confirm that these criteria (at least 3 acceptable tests with the 2 highest acceptable (largest and next largest) efforts within 150 mL of vital capacity) have been achieved.

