The third secondary endpoint will be change from baseline to Day 197 in percent predicted SVC. If the number of deaths across both treatment arms is  $\geq 3$  (i.e.,  $\geq 5\%$  deaths out of a total of 60 patients in the mITT population), the primary inference will be based on the JRT methodology with MI to impute missing data; ANCOVA with MI for change from baseline will be used to obtain the estimates, and nominal p-values will be presented. If the number of deaths is  $< 3$  (i.e.,  $< 5\%$  deaths out of a total of 60 patients in the mITT population), ANCOVA with MI will be used as the primary analysis of this endpoint. The ANCOVA model will include treatment group as a fixed effect and covariates for baseline percent predicted SVC, baseline disease duration since symptom onset, and use of riluzole or edaravone. Treatment differences at other visits will also be derived from the model for exploratory purpose.

CONFIDENTIAL

The information contained herein may not be used, disclosed, or published without the written consent of Biogen MA Inc.

The secondary efficacy endpoints, time to death or permanent ventilation and time to death, will each be analyzed as time to event endpoints. Kaplan-Meier estimates of the cumulative probability of event occurrence over time will be determined. Treatment comparison will be based on a stratified log rank test. A Cox regression model will be used to obtain the hazard ratio and 95% confidence intervals for each of these endpoints. The analysis for each endpoint will also be repeated for the non-mITT population with nominal p-values presented.

[REDACTED]

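### Table 3 footnote 10 both requires and forbids the facemask for SVC when mask use differs between screening and baseline

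*Protocol*

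**What the plan says.** Protocol Table 3 (Section 4.2) schedules SVC at screening and again predose on Day 1, then at every later dosing visit and at the end-of-study visit. The whole SVC row carries footnote 10, which sets the interface in two consecutive sentences:

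- The first covers participants who wore a mask: "If a facemask is used at screening and/or baseline it should be used for all SVC assessments for the duration of the study".
- The second covers those who did not, and points the other way: "If a facemask is not used at screening and/or baseline it should not be used for the duration of the study".

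Section 13.1.2 describes the SVC test without mentioning a facemask and refers to a separate document: "The procedure will be performed according to the study Pulmonary Procedure Manual". That manual is not part of the protocol.

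Section 7.1.3 allows screening and baseline to take place at different sites: "Participants who complete screening at screening-only sites and are deemed eligible for participation in Part C will be transferred to a full participation site". It also allows transfers between full treatment sites before randomization.

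Section 16.2.1.2.2 makes the SVC change a formally tested endpoint: "The third secondary endpoint will be change from baseline to Day 197 in percent predicted SVC". It follows CSF total SOD1 protein and plasma NfL in the testing order. Baseline percent predicted SVC is also a covariate in its ANCOVA.

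**The concern.** The footnote is evidently meant to keep one interface per participant. Because both sentences use the same inclusive connective, they overlap as soon as the two early visits differ. A site with such a participant then has two opposite instructions and no tie-break, and different sites could settle it differently.

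What is at stake is whether the change score compares like with like. If a participant's baseline is taken with one interface and Day 197 with the other, the recorded change includes any difference between interfaces as well as any change in the participant. The same baseline value enters the ANCOVA as a covariate. This is the first clinical endpoint in the secondary testing sequence, so a rule written to standardize its measurement should not be able to do the opposite.

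**Working it through.** The plan states no figure on this point, so the check is one of logic.

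**Step 1: the conditions.** Let S mean that a mask was used at screening and B that a mask was used at baseline. Read literally, the first sentence is triggered by S or B, and the second by not-S or not-B.

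**Step 2: the four combinations.**

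| Screening | Baseline | First sentence | Second sentence | Result |
|---|---|---|---|---|
| mask | mask | use | not triggered | consistent |
| none | none | not triggered | do not use | consistent |
| mask | none | use | do not use | contradictory; following the first sentence gives masked follow-up against an unmasked baseline |
| none | mask | use | do not use | contradictory; following the second sentence gives unmasked follow-up against a masked baseline |

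Two of the four combinations are contradictory. In each of these, one instruction keeps follow-up matched to baseline and the other breaks the match.

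**Step 3: other readings of the connective.**

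- If the connective is read as *and* in both sentences, a discordant participant falls under neither and has no instruction.
- If the second sentence is read as the plain negation of the first (no mask at either visit), the contradiction goes, but the mask is then required in both discordant cases. A participant masked at screening and unmasked at baseline still has masked follow-up against an unmasked baseline.

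None of these readings ensures that follow-up matches baseline.

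**Step 4: does anything else settle it?** Section 13.1.2 does not mention the mask, and no other protocol text names a governing visit.

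**Step 5: how it would enter the analysis.** Under Section 9.2, Part C participants are randomized on Day 1 after the predose assessments, and SVC is one of those. Whether the two early visits differ is therefore fixed before allocation.

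Under Section 16.2.1.2.2, inference on SVC uses the joint rank test if there are 3 or more deaths in the mITT population. Section 16.2.7 assumes 60 mITT participants and Week 28 survival of 90% on BIIB067 and 82% on placebo. At 2:1 this is 40 and 20 participants, so expected deaths are 40 × 0.10 + 20 × 0.18 = 4.0 + 3.6 = 7.6. On the plan's own assumptions, the rank-based test is the expected route. Affected change scores would enter the ranks, while the ANCOVA would still supply the estimates.

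**The case against.** The best defence is that the footnote, followed in order, prevents the problem. A mask used at screening must be used at all SVC assessments, and the Day 1 test is one of them. No mask at screening means none for the rest of the study, which again covers Day 1. A difference between the visits then arises only after a lapse or a change at baseline. This stands as a limit on how often the case should occur. It does not remove the contradiction: the words giving baseline equal standing would then do no work, and the footnote still gives opposite instructions once the visits differ.

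It is also fair that the Pulmonary Procedure Manual may settle the matter. If so, the footnote would still need to agree with it.

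Two stronger conclusions might be drawn, and the documents support neither.

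- **That the site-transfer provisions make discordant cases likely.** Section 7.1.3 makes them possible. It does not say that sites use different interfaces or how many participants transfer.
- **That the treatment comparison would be shifted by some estimable amount.** The protocol gives no mask effect. A shift computed for one arm alone would not be the treatment contrast, and discordant cases in opposite directions could offset each other. An arm-mean shift would not carry directly into a rank-based p-value. SVC is formally tested only if the primary endpoint, CSF SOD1 and plasma NfL all succeed first.

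**Conclusion.** The contradiction is real and stands in the current protocol text. It affects only participants whose mask use differs between screening and baseline. For them, one of the two instructions yields a change score that mixes interfaces.

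The expected consequence is added noise in a secondary endpoint. That it is non-differential rests on two things: the discordance precedes randomization, and the staff who then choose between the instructions are blinded to treatment. Neither the number of such participants nor the size of the measurement error can be derived from the protocol, so no numerical impact is claimed. Severity is minor. The primary analysis is not touched.

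**What to change.** Replace the two facemask sentences of Table 3 footnote 10 with one rule that names a single reference visit, for example:

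*The Baseline SVC should use the same interface (facemask or none) as screening; whichever interface is used at the Baseline predose SVC is used for every later SVC, including home assessments.*

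This keeps the aim of one interface throughout and supplies the missing tie-break. It also ties follow-up to the value from which change is measured. Home assessments are already covered by the present wording; naming them simply makes the rule plain to staff who did not do the baseline test. The Pulmonary Procedure Manual should be checked for agreement.

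The cost is a footnote edit and a memo to sites. No assessment is added and the analysis does not change.

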-  Not required if collected during Screening Visit 1.
-  Including blood samples for HIV, HCV, and HBV tests, and platelet and coagulation tests. Coagulation tests may be repeated at the local laboratory once if, in the opinion of the Investigator, values of the initial tests are only slightly out of range. Participants with nonclinically significant and stable out-of-range values for coagulation tests may be eligible to enroll in the study at the discretion of the Investigator, and after a consultation with the Sponsor.
-  Limited physical examination will be conducted at the Investigator's discretion.
-  To be assessed at 3 and 6 hours postdose.
-  To be assessed within an hour prior to drawing PK blood samples at 2 and 4 hours postdose.
-  Triplicate 12-lead (paper) ECGs will be obtained after the participant has rested in a supine position for at least 10 minutes. The first ECG will be interpreted, and the last 2 will be checked for consistency and quality.
-  Use the "Since Last Visit" version of C-SSRS.
-  For women of childbearing potential only.
-  To confirm postmenopausal status in postmenopausal female participants.
-  Day 29 only.
-  LP will be performed to collect CSF samples for PK, PD, safety, and biomarker analysis. The results of the most recent (i.e., obtained at Screening or other visit during the study) coagulation tests and platelet count must be reviewed before each LP can be performed. Should the results suggest, in the opinion of the Investigator, that an LP may be safely performed, then no further laboratory values need to be reviewed. However, should, in the opinion of the Investigator, repeat coagulation and platelet tests be clinically indicated, then these tests may be done locally to facilitate timely review. Results of any repeat tests must be available before the LP can be performed.
-  To be collected at Day 29 only. Participants will remain under observation in the clinic for approximately 1 hour after the LP procedure and will receive a safety FU telephone contact ~24 hours after the procedure.

- 
-  To be collected at 1, 2, 4, and 6 hours postdose.

CONFIDENTIAL

The information contained herein may not be used, disclosed, or published without the written consent of Biogen MA Inc.

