17. Presence of risk for increased or uncontrolled bleeding and/or risk of bleeding that is not managed optimally and could place a participant at an increased risk for intraoperative or postoperative bleeding. These could include, but are not limited to, anatomical factors at or near the LP site (e.g., vascular abnormalities, neoplasms, or other abnormalities) and underlying disorders of the coagulation cascade, platelet function, or platelet count (e.g., hemophilia, Von Willebrand's disease, liver disease).
18. Anticipated need, in the opinion of the Investigator, for administration of any antiplatelet or anticoagulant medication (e.g., clopidogrel) for 7 days before or 48 hours after an LP.
19. Presence of an implanted shunt for the drainage of CSF or an implanted CNS catheter.
20. Clinically significant abnormalities in hematology or clinical chemistry parameters, as determined by the Investigator, which would render the participant unsuitable for enrollment. For a list of normal, acceptable, and exclusionary ranges, please refer to the study reference guide.
21. Clinically significant, as determined by the Investigator, 12-lead ECG abnormalities, including corrected QT interval using Fridericia's correction method of > 450 ms for males and > 470 ms for females.
22. Inability to comply with study requirements.
23. Other unspecified reasons that, in the opinion of the Investigator or Sponsor, make the participant unsuitable for enrollment.

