13. History of allergies to a broad range of anesthetics.
14. Presence of risk for increased or uncontrolled bleeding and/or risk of bleeding that is not managed optimally could place a participant at an increased risk for intraoperative or postoperative bleeding. These could include, but are not limited to, anatomical factors at or near the LP site (e.g., vascular abnormalities, neoplasms, or other abnormalities) and underlying disorders of the coagulation cascade, platelet function, or platelet count (e.g., hemophilia, Von Willebrand's disease, liver disease).
15. Anticipated need, in the opinion of the Investigator, for administration of any antiplatelet or anticoagulant medication that cannot be safely held before and/or after an LP procedure according to local or institutional guidelines and/or Investigator determination.
16. Presence of an implanted shunt for the drainage of CSF or an implanted CNS catheter.
17. Clinically significant abnormalities in hematology or clinical chemistry parameters, as determined by the Investigator, which would render the participant unsuitable for

CONFIDENTIAL

The information contained herein may not be used, disclosed, or published without the written consent of  
Biogen MA Inc.

enrollment. For a list of normal, acceptable, and exclusionary ranges, please refer to the study reference guide.

18. Clinically significant, as determined by the Investigator, 12-lead ECG abnormalities, including corrected QT interval using Fridericia's correction method of  $> 450$  ms for males and  $> 470$  ms for females.
19. Inability to comply with study requirements.
20. Other unspecified reasons that, in the opinion of the Investigator or Sponsor, make the participant unsuitable for enrollment.

CONFIDENTIAL

The information contained herein may not be used, disclosed, or published without the written consent of Biogen MA Inc.

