#### **16.2.4.2.4. Electrocardiogram**

The number and percentage of participants with shifts to categorical values (abnormal not AE, or abnormal AE) will be summarized by treatment group.

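### Part C takes three centrally read ECGs per time point but interprets only the first, and never says that QTcF is the mean of the three

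*Protocol*

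**What the plan says.** Four places in the protocol bear on the point.

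- **Collection and reading (Section 4.2, Table 3, footnote 16).** In Part C, "Triplicate 12-lead ECGs will be obtained after the participant has rested in a supine position for at least 10 minutes". On reading: "All ECGs will be centrally read; ECGs will be read by the Investigator at collection and then sent to a central ECG reader". The central reader is also given the task of confirming eligibility at Screening. The footnote ends: "The first ECG will be interpreted, and the last 2 will be checked for consistency and quality".
- **Timing (Table 3, footnote 17).** Postdose ECGs are taken just before the PK draws at 2, 4 and 6 hours, on Day 1 and Day 85. In the amendment history, the rationale for the ECG and PK timing mentions support for a possible waiver of a thorough QT analysis.
- **Eligibility (Section 8.2.2, item 18).** The exclusion reads "Clinically significant, as determined by the Investigator, 12-lead ECG abnormalities, including corrected QT interval", by Fridericia's correction, above 450 ms for men and above 470 ms for women.
- **Analysis (Section 16.2.4.2.4).** "The number and percentage of participants with shifts to categorical values (abnormal not AE, or abnormal AE) will be summarized by treatment group".

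None of these says whether the QTcF for a time point is the first tracing's value or the mean of three.

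**The concern.** QTcF is a continuous measurement with random error between tracings, and at Screening it is set against a fixed limit. The usual statistical reason for recording three tracings is to average out part of that error. Footnote 16 gives the second and third tracings a different job, a check on consistency and quality. Such a check can catch a gross error, but it does not make the retained value more precise.

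Two uses are exposed. At Screening, a candidate whose true QTcF lies near the limit is more likely to be read on the wrong side of it. At the PK-timed points, each QTcF carries more noise than the recorded data require, in a part of the study with about 33 placebo participants. The statistical analysis plan could define an averaged value for analysis. It could not repair a Screening decision already taken on a single tracing, so the wording of the footnote matters for eligibility.

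**Working it through.** The protocol states no SD, power or sample size for QTcF, so there is no figure of its own to reproduce. The check compares one tracing with the mean of three.

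**Inputs from the protocol.** Three tracings per time point and the first-tracing rule (Table 3, footnote 16); an upper limit of 450 ms for men (Section 8.2.2, item 18).

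**Assumptions, not protocol figures.** Single-tracing error SD of 5, 8 or 10 ms; correlation ρ of 0, 0.5 or 0.8 between the errors of tracings taken at the same time point; normal errors.

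**Step 1: error of the mean of three.** SD(mean) = SD × √((1 + 2ρ)/3).

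- ρ = 0: factor √(1/3) = 0.577, a 42% reduction.
- ρ = 0.5: factor √(2/3) = 0.816, an 18% reduction.
- ρ = 0.8: factor √(2.6/3) = 0.931, a 7% reduction.

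The reduction depends only on ρ, not on the SD. At ρ = 0 the variance falls by two thirds, but the SD, which governs how far a reading strays, falls by 42%.

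**Step 2: crossing the limit.** For a man with true QTcF 440 ms, P(reading > 450) = 1 − Φ(10/SD) on one tracing and 1 − Φ(10/SD(mean)) on the mean.

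| Assumed SD | One tracing | Mean, ρ = 0 | Mean, ρ = 0.5 | Mean, ρ = 0.8 |
|---|---|---|---|---|
| 5 ms | 2.3% | 0.03% | 0.7% | 1.6% |
| 8 ms | 10.6% | 1.5% | 6.3% | 9.0% |
| 10 ms | 15.9% | 4.2% | 11.0% | 14.1% |

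By symmetry the same rates apply to a true value of 460 ms read at or below 450 ms. Nearer the limit the contrast is smaller. For a true value of 445 ms the single-tracing rates are 15.9%, 26.6% and 30.9%. The mean of three gives 4.2%, 14.0% and 19.3% at ρ = 0, and 11.0%, 22.2% and 27.0% at ρ = 0.5.

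**Step 3: change from baseline.** If the errors at the two visits are independent, the error SD of a change is √2 times that of one value, so the proportional gain is the same. With a single-tracing SD of 8 ms it falls from 11.3 ms to 6.5 ms (ρ = 0), 9.2 ms (ρ = 0.5) or 10.5 ms (ρ = 0.8).

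The direction is the same throughout: the mean is more precise unless replicate errors are perfectly correlated. The size depends on two quantities that the protocol does not give.

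**The case against.** The strongest reply is that footnote 16 never says QTcF comes from the first tracing. To interpret an ECG may mean only the qualitative clinical reading that feeds the shift table in Section 16.2.4.2.4, while the intervals are taken from all three tracings, since all are centrally read. This stands in part: use of a single tracing is the plain reading, not a stated fact. It does not remove the point, because a footnote that leaves the source of an eligibility value open needs settling either way.

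The crossing rates also leave out safeguards. Exclusion 18 sits within the Investigator's judgement of clinical significance, the central reader confirms eligibility, discordant tracings could be flagged by the consistency check, and Section 9.1 allows one rescreening. This stands in full: the rates describe readings, not wrongly excluded or wrongly admitted participants.

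A reader might infer two stronger claims that the protocol does not support.

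- **That QTcF will not be analysed as a number.** Section 16.2.4.2.4 is a one-sentence outline and does not rule out numeric summaries. Those are commonly left to the statistical analysis plan, and the recorded interest in a thorough QT waiver suggests that quantitative work was in view.
- **That Parts A and B have the same defect.** Tables 1 and 2 share the first-tracing rule, but for paper ECGs ("Triplicate 12-lead (paper) ECGs will be obtained after the participant has rested in a supine position for at least 10 minutes") and with no central reading stated. The argument that the readings are already in hand therefore does not carry over.

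**Conclusion.** The point holds for Part C as a minor matter of measurement precision and clarity. Three tracings are recorded and all are centrally read, yet the only stated rule interprets the first, and nothing says that a mean is used for QTcF.

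If one tracing does supply QTcF, averaging would lower its error SD by at most 42%. That figure needs independent replicate errors. Tracings taken close together may share error, and the gain is then about 18% at a correlation of 0.5 and 7% at 0.8. It would be tempting to present 42%, or any of the crossing rates, as this trial's actual loss. The protocol gives neither the replicate SD nor the correlation, so they show a range under assumptions and no more.

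The primary endpoint, alpha and power are unaffected, and no two statements in the protocol contradict each other on this point.

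**What to change.** Amend footnote 16 of Table 3, for Part C only, to say that:

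1. heart rate, PR, QRS and QTcF at each time point are the mean of the three centrally read tracings;
2. the qualitative interpretation stays as it is now;
3. at Screening, the mean QTcF is the value compared with the existing limits in exclusion 18, which do not change and still apply within the Investigator's judgement.

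The cost is interval measurement on two further tracings per time point that the central reader already receives. Participants have no extra procedure. Tables 1 and 2 and Section 16.2.4.2.4 need no change on this account.
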